4.2.2 Formal Criteria for Interim Efficacy Analyses

If conducted, the interim analysis will apply a 2-sided alpha level of 0.010 (75% information fraction), and at the final analysis at a 2-sided alpha of 0.022 with the overall Type I error rate at 2-sided alpha of 0.05. Efficacy boundaries for early stopping of the study for efficacy are based

¹ Subjects who were active in the treatment periods of this protocol as of 13 March 2020 will be assessed on a case-by-case basis by the Sponsor for inclusion of populations for adaptive, interim, and final analyses. All decisions will be documented and presented in the clinical study report.

on a Lan-DeMets spending function, with an O'Brien-Fleming boundary (GD-INFO; EAST[®], Cytel, Version 6.5). The corresponding non-binding futility boundary is provided as p-value less than or equal to 0.227 for the interim analysis (Lan-DeMets: O'Brien-Fleming).

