7 GENERAL CONSIDERATIONS FOR DATA ANALYSES

Given the crossover design utilized for this study, efficacy and safety summary tables will follow the general format that baseline and post-baseline data will be presented by the assigned treatment condition when those data are observed during the treatment period. Treatments will be labeled as “Treprostinil” and “Placebo” to correspond with the assigned treatment condition.

Any efficacy and safety data that are collected during the washout period between Periods 1 and 2 will be presented for the assigned treatment condition from Period 1. Any follow-up data collected after Period 2, while on this study, will be assigned to Period 2. Subjects who are not retained will not be replaced during the study.

For continuous variables, the summary statistics will include the mean, standard deviation, median, lower quartile, upper quartile, minimum, and maximum. Statistics will be expressed using the level of precision in which the variable was collected. For discrete variables, summaries will include the frequency and percent in each category. Whenever practical, categories of discrete variables will be ordered and labeled as they appear in the case report form (CRF), and all categories represented on the CRF will be included in summaries, even when they do not apply to any patients in the study.

For data collected on a fixed schedule, the nominal time point will be used for summarization. Evaluations from Unscheduled Visits are to be mapped to Scheduled Visits to the extent possible per the protocol-specified windows. Repeat or redundant observations within an assessment window and observations that do not fall within any predefined assessment window will be excluded from summaries. If an evaluation is repeated, such as to confirm an observed aberrant laboratory value, the analyses will use the later value if within the protocol-specified window.

Unless otherwise specified, all final statistical tests will be 2-sided at alpha level 0.05 if the interim analysis is not conducted, and 0.022, if conducted. All tables will be presented in landscape format. For practical reasons, the point size may be reduced to (but not less than) 7 point for tables that contain too much information to fit into a single page. SAS[®] version 9.4 or higher will be used. The Sponsor's Biostatistics Department will analyze the efficacy and safety data.

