12.4 CONTINGENT PARALLEL DESIGN ANALYSIS PLAN

The RIN-PH-304 study is an adaptive study with a (fully blinded) decision for design modification based on enrollment and missing data metrics. Following a formal and documented decision to switch from the Original Crossover Design to the Contingent Parallel Design, the following modifications will be applied to those sections specified in the main body of this SAP with the Original Crossover Design. To minimize repetition, this section will cover only those sections affected by a decision to switch to the Contingent Parallel Design, that is:

- If no modifications are required to a section in the main body of the SAP, no mention will be made below. For example, Section 2 (Study Objectives and Endpoints) requires no modification under switch to a parallel design.
- If a modification will be necessary, the affected section number and the replacement text are provided below. The updated text will then supersede the current text in the main body of the SAP. Text within an affected section that does not require modification will not be repeated below.

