12.4.2 Interim Efficacy Analysis

Section 4.2: A single interim efficacy analysis will be conducted when 75% of the subjects (ie, ~235 subjects) have completed the 12-week Treatment Period if both of the following criteria are met: a) the expected time to randomize the final (314th) subject is greater than 6 months; b) at least 90% of the 6MWD data is present for Period 1: Baseline and Week 12 for these subjects.

Section 4.2.1: Prior to any planned interim analysis being performed, the following steps will be followed to estimate the expected time to randomize the final (314th) subject:

[REDACTED]

Section 4.2.2: If conducted with exactly 75% information fraction, the interim analysis will apply a 2-sided alpha level of 0.019, and at the final analysis at a 2-sided alpha of 0.044 with the overall Type I error rate at 2-sided alpha of 0.05; the actual information fraction at the time of the interim analysis will be used to calculate the 2-sided alpha level that will be applied. Efficacy boundaries for early stopping of the study for efficacy are based on an O'Brien-Fleming spending function (PASS 12, NCSS, Version 12.0). There will be no corresponding futility boundary for the interim analysis.

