12.4.3 General Considerations For Data Analyses

Section 7: If the study design is changed to a parallel design, efficacy and safety summary tables will follow the general format that baseline and post-baseline data will be presented by the assigned treatment group when those data are observed. Treatments will be labeled as "Treprostinil" and "Placebo" to correspond with the assigned treatment group.

Efficacy and safety data collected after study discharge (after Period 1) will not be presented.

Section 7.1: If the study design is changed to a parallel design for this study, only the Period 1 baseline for efficacy measurements will be used. Except for actigraphy measurements, the baseline value will be defined as the non-missing value immediately prior to dosing with study drug for Period 1: Day 1. The baseline period for actigraphy measurements will be the last 7 days during the washout period prior to the day of dosing on Day 1. In the event that the washout period is less than 7 days then only the non-dosing days will be used to derive a baseline average.

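### If the trial switches to the parallel design and runs its interim look, the readable SAP leaves three final levels in force: 0.044 for the primary test, a leftover 0.022 as the only readable level for the key secondaries, and a 0.05 gate

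*SAP*

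**What the plan says.** Four parts of the SAP bear on the level of the final tests once an interim efficacy analysis has been run.

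- **Section 7 (general considerations):** a default that gives way wherever another level is specified: "all final statistical tests will be 2-sided at alpha level 0.05 if the interim analysis is not conducted, and 0.022, if conducted". The figure is the crossover one. Section 4.2.2 states that "the interim analysis will apply a 2-sided alpha level of 0.010 (75% information fraction), and at the final analysis at a 2-sided alpha of 0.022".
- **Section 12.4.2 (parallel design, replacing 4.2.2):** a look at exactly 75% information is tested at 2-sided 0.019. The second stage is set as follows: "at the final analysis at a 2-sided alpha of 0.044 with the overall Type I error rate at 2-sided alpha of 0.05". For a look at any other fraction, this section provides that "the actual information fraction at the time of the interim analysis will be used to calculate the 2-sided alpha level that will be applied".
- **Section 12.4 (how the appendix works):** where replacement text is given, it overrides the main body. Otherwise the main body stands: "Text within an affected section that does not require modification will not be repeated below". Section 7 is one of the affected sections. Its replacement in 12.4.3 begins "If the study design is changed to a parallel design, efficacy and safety summary tables will follow the general format" and covers table layout, treatment labels, data collected after discharge and the baseline definition. It says nothing about the alpha sentence.
- **Section 7.7 (multiplicity), which 12.4 does not mention:** the secondaries are tested formally once the primary is significant at 2-sided 0.05. The text after this is redacted. Section 9.3 says the key secondaries are tested in order, and its readable text gives no level.

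**The concern.** Under the appendix's own rule, a number calculated for the crossover design carries into a design that has its own boundary. For the primary test, 12.4.2 overrides it. For the key secondaries, the readable text offers no other level after an interim, so they would be tested at 0.022, about half the level that the parallel boundary leaves for the final stage. The 7.7 gate errs in the other direction. Read literally, it treats the primary as significant for opening the secondaries at 0.05, although 12.4.2 has already spent part of the 0.05 at the interim.

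A fixed figure is also out of place beside a rule that recalculates the level from the actual information fraction. If these sentences are not aligned before unblinding, the level for a borderline secondary result, or for a primary p between 0.044 and 0.05 at the gate, could be argued over once the data are known.

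**Working it through.** **Inputs.** Interim 0.019, final 0.044, overall 0.05, 75% information (SAP 12.4.2). Section 7 default 0.022. Section 7.7 gate 0.05. Parallel design: 133 per arm, difference 30 m, SD 75 m, at least 90% power at 2-sided 0.05 (SAP 5.1). The 20 m effect used below is an assumption, not a figure from the plan.

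**1. Reproducing the plan's pair.** Lan-DeMets spending of O'Brien-Fleming type, with 0.025 per tail, spends at information t = 0.75

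2 × [1 − Φ(2.2414/√0.75)] = 2 × [1 − Φ(2.588)] = 0.00965 per tail,

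which is 0.0193 2-sided. Solving for the final boundary, with correlation √0.75 = 0.866 between the two statistics, gives 0.0442 2-sided. Both match 0.019/0.044 as printed. The final level moves with the information at the interim: 0.0455 at 70%, 0.0429 at 80%, 0.0414 at 85%.

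**2. Overall type I error.** This is 1 − P(|Z1| < c1, |Z2| < c2) under the null, with the same correlation and c1 = 2.346 (0.019).

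| Final level | c2 | Overall 2-sided error |
|---|---|---|
| 0.044 (12.4.2) | 2.014 | 0.0496 |
| 0.022 (Section 7) | 2.290 | 0.031 |
| 0.05 (7.7 gate) | 1.960 | 0.055 |

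**3. Power for the 6MWD test.** Standard error = 75 × √(2/133) = 9.197 m. At 30 m the final statistic has mean 30/9.197 = 3.262, and the interim statistic 3.262 × 0.866 = 2.825. Power is the chance of crossing at either look.

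- Final level 0.044: 89.8%.
- Final level 0.022: 84.9%.
- For comparison, one fixed test at 0.05 (normal approximation): 90.4%, in line with the stated 90%.

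The smallest significant final difference is 2.014 × 9.197 = 18.5 m at 0.044 and 2.290 × 9.197 = 21.1 m at 0.022.

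**4. How often the choice between 0.022 and 0.044 decides the result, counting early stopping at the interim.**

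- True 30 m: 0.8983 − 0.8490 = 0.049, or 4.9% of trials.
- Assumed 20 m: 0.5754 − 0.4842 = 0.091, or 9.1% of trials.

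Steps 3 and 4 use the 6MWD test because it is the only one with design figures. They show the cost of the wrong level; they are not estimates for the secondaries.

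**5. Where 0.022 comes from.** Halving the values from step 1 gives per-tail levels of 0.0096 and 0.0221, which round to the 0.010 and 0.022 in 4.2.2. As a 2-sided pair, 0.010/0.022 spends only 0.0256 overall, not 0.05.

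**The case against.** Section 7 opens by yielding to anything specified elsewhere, 12.4.2 specifies 0.044, and 12.4 says replacement text overrides the main body. A reader might infer from Section 7 and 12.4.2 that the primary test has two competing levels. The documents do not support that: the primary has one answer, 0.044 or its recalculated value.

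A reader might also infer that the key secondaries are certain to be tested at the wrong level. That cannot be confirmed either. The redacted part of 7.7 is where their level would normally be set, and 12.4.2 refers to the final analysis without limiting itself to the primary, so 0.044 can be argued to reach the secondaries already. What stands is that no readable sentence says so, while Section 7 speaks of all final tests.

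Three further points are fair. First, the situation needs two triggers. The design switches only if 6MWD and actigraphy are both below 85% present at Week 25. The interim is then run only if more than 6 months are expected to the last randomization and at least 90% of the 6MWD data are present. Second, a mistaken 0.022 is conservative: it costs power and raises no false-positive risk. Third, if 0.022 is a one-sided value under a 2-sided label, correcting it would turn the Section 7 figure into 0.044, and the gap would vanish at exactly 75% information. A fixed number would still conflict with the recalculation rule, and the 0.05 gate would remain.

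**Conclusion.** The inconsistency is real but limited. After a switch and an interim, the readable plan has 0.044 for the primary, 0.022 as the only readable level that clearly covers the key secondaries, and 0.05 at the gate. The 0.022 is needlessly strict: on the 6MWD test it would leave about 0.019 of the 0.05 unspent (0.05 − 0.031) and cost 4.9 percentage points of power. The 0.05 gate is too lenient: if it were used to judge the primary after an interim at 0.019, the overall error would be 0.055.

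The shortfall from 90% should not all be put down to 0.022. Power is already 89.8% at 0.044, because the 266 subjects were sized for a single test at 0.05.

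The figures assume an interim at exactly 75% information, 133 evaluable subjects per arm, an SD of 75 m and normal test statistics. The statement about the key secondaries rests on the unredacted text alone. The plan should be corrected before unblinding, because the ambiguity is cheap to remove then and hard to settle credibly afterwards.

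**What to change.** 1. In SAP 12.4.3, add replacement text for the Section 7 alpha sentence. Unless otherwise specified, final tests are 2-sided at 0.05 if no interim efficacy analysis is run. If one is run, they are at the final-stage level from 12.4.2: 0.044 at exactly 75% information, otherwise recalculated from the actual fraction.
2. Add matching replacement text for 7.7, so that the gate uses that same level and not a fixed 0.05.
3. State that this one level applies to the primary test, the gate and the ordered key secondaries. If the redacted part of 7.7 already sets a level for the secondaries, align it with this text.
4. Separately, check the 2-sided label on 0.010/0.022 in 4.2.2 and on the 0.022 in Section 7 against the software output.

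The cost is a few sentences in the SAP appendix before unblinding. No patients and no new analyses are needed.

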7.1 BASELINE

Given the crossover design utilized for this study, Periods 1 and 2 each have a different baseline for efficacy measurements: Period 1: Day 1 and Period 2: Week 14. With the exception of actigraphy measurements, the baseline value will be defined as the non-missing value immediately prior to dosing with study drug for Period 1: Day 1 and Period 2: Week 14. The baseline period for actigraphy measurements will be the last 7 days during the washout period prior to the day of dosing on Day 1 and Week 14. In the event that the washout period is less than 7 days then only the non-dosing days will be used to derive a baseline average.

For safety evaluations, the baseline will be defined as the last evaluation closest, but prior to, the first dose of study drug during the low dose run-in period.

7.2 CHANGE FROM BASELINE

For parameters measured at baseline, the variables of interest are the change from baseline of the original measurements. Unless otherwise specified, all changes from baseline (for all variables where this is applicable) will be calculated as follows:

$$\text{Change from baseline} = \text{Post baseline} - \text{baseline}$$

7.3 STUDY DAY

Study day will be calculated relative to first dose of study drug (Day 1), after randomization. Specifically:

$$\text{Study day before dosing} = (\text{Date of occurrence} - \text{Date of first dose of study drug}).$$

$$\text{Study day on or after dosing} = (\text{Date of occurrence} - \text{Date of first dose of study drug}) + 1.$$

7.4 COVARIATES

Efficacy analyses will include the assigned treatment sequence and period order as covariates. Change from baseline analyses will include the baseline measurement as a continuous covariate.

7.5 EXAMINATION OF SUBGROUPS

Primary and secondary efficacy analyses will be conducted on the FAS. Subgroup analyses will be performed to explore the efficacy of treprostinil in different subject populations. The subgroups will include, but not be limited to:

- age (<65, ≥65 years);
- sex (males, females);
- race (White, Black or African-American, Asian, American Indian or Alaskan Native, Native Hawaiian or Other Pacific Islander);
- ethnicity (Hispanic or Latino, non-Hispanic or Latino);
- age at WHO Group 3 PH-COPD diagnosis (date of diagnosis minus date of birth, in years, by quartiles);
- pulmonary vascular resistance (PVR; during screening, in quartiles);
- mean pulmonary artery pressure (mPAP; during screening, in quartiles);
- baseline (Day 1) 6MWD (≤350 meters versus >350 meters);
- baseline (Day 1) Borg dyspnea score (in quartiles).

Unless otherwise prespecified, continuous covariates will be presented by quartiles.

Comparative results will be presented using point estimates and associated 95% CIs both in tables and forest plots. Because the study was not designed to have high power for small or even moderate sized subgroups, these analyses will be considered exploratory. No Type 1 error adjustments will be performed for these subgroup analyses.

7.6 PREMATURE DISCONTINUATION AND MISSING DATA

Investigators and site staff are to encourage all subjects to continue their participation in the study and complete all study procedures and study visits as indicated by the study protocol unless the subject provides a written withdrawal of consent from the study. A subject's discontinuation from study drug does not mean discontinuation from the study. If study drug is discontinued for a randomized subject, the subject will be encouraged to actively continue to

return for all study visits per the study protocol, and the Investigator will continue all reasonable efforts to obtain the subject's data.

Patients may not complete the full treatment periods for the following reasons: death, lost to follow-up, study terminated by Sponsor, COVID-19 truncation, or withdrawal of consent. All available data from all patients will be used as detailed in this analysis plan. In addition, subjects may be too ill to perform assessments, such as the 6MWT or Borg, resulting in missing data for that assessment.

Methods for imputation and handling missing data, when applicable, will be described in the sections for the particular outcome.

7.7 MULTIPLE COMPARISONS AND MULTIPLICITY

A gatekeeper strategy will be employed to address multiple comparisons. Secondary endpoints will be formally tested only if the primary endpoint is statistically significant. If the primary analysis of treprostinil vs placebo change from Baseline to Week 12 is statistically significant at a 2-sided alpha level of 0.05, showing superiority of treprostinil over placebo, then the secondary endpoints will be formally tested.

[REDACTED]

- [REDACTED]
- [REDACTED]
- [REDACTED]
- [REDACTED]
- [REDACTED]

[REDACTED]

Other secondary endpoints, including change in QOL, based on the SGRQ and UCSD SOBQ, and PGA will not have formal statistical testing.

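### SAP 7.7 states the gate to secondary testing as 0.05 with no interim condition, which conflicts with the stricter final level that applies to the primary after an interim look

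*SAP*

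**What the plan says.** SAP 7.7 describes the gate twice. The first statement has no number: "Secondary endpoints will be formally tested only if the primary endpoint is statistically significant". The next sentence supplies one: the gate opens if the primary comparison at Week 12 "is statistically significant at a 2-sided alpha level of 0.05" and shows superiority of treprostinil. Neither sentence mentions the interim analysis.

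Other sections make the level of the final test depend on the interim:

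- SAP 7 (general considerations) runs final tests "at alpha level 0.05 if the interim analysis is not conducted, and 0.022, if conducted". This is a default that applies only where no other level is given.
- SAP 4.2.2 (crossover) pairs an interim level of 0.010 at 75% information with a test "at the final analysis at a 2-sided alpha of 0.022 with the overall Type I error rate at 2-sided alpha of 0.05".
- SAP 12.4.2 (parallel) pairs an interim level of 0.019 with a test "at the final analysis at a 2-sided alpha of 0.044". It recalculates the interim level if the information fraction is not exactly 75%.

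Appendix 12.4 says that sections it does not mention need no modification. It does not mention 7.7, so the 0.05 gate carries over to the parallel design. It also leaves the 0.022 in Section 7 in place.

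SAP 9.3 and protocol 10.3 and 10.3.3 make secondary testing conditional on a significant primary without tying that to an interim-dependent level. Both protocol sections promise family-wise error control at 0.05.

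**The concern.** Suppose the interim is run, the trial continues, and the final primary p-value is 0.03 in the crossover design or 0.047 in the parallel design. The primary has failed at its allocated level, yet the numeric rule in 7.7 lets formal secondary testing go ahead. The default in Section 7 does not clearly override this, because it yields wherever another level is specified, and 7.7 specifies one.

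Two things are at stake. First, the plan gives two answers to the question of whether the secondaries may be claimed, and the dispute would arise only after unblinding. Second, a gate wider than the primary's own rejection region is an extra route to a false claim, so the promised family-wise control needs checking.

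**Working it through.** **Inputs.** Interim and final levels: 0.010 and 0.022 (SAP 4.2.2), 0.019 and 0.044 (SAP 12.4.2). Gate: 0.05 (SAP 7.7). Information fraction: 0.75. For the crossover effect sizes: N = 124 and SD of differences 85 m (SAP 5.1).

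**Method.** Under the null, the interim and final statistics Z1 and Z2 are bivariate normal with correlation √0.75 = 0.866. For two-sided levels a1 and a2, the critical values are c = Φ⁻¹(1 − a/2), and

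overall(a1, a2) = 1 − P(|Z1| < c1 and |Z2| < c2).

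**Step 1: the plan's own levels.**

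- Parallel, 0.019 and 0.044: c1 = 2.346, c2 = 2.014, overall = 0.0496. This agrees with the stated 0.05. O'Brien-Fleming-type spending of 0.025 per tail gives 2[1 − Φ(2.241/0.866)] = 0.0096 per tail at the interim, or 0.0193 two-sided, with a two-sided final level of 0.0442.
- Crossover, 0.010 and 0.022 as labelled (two-sided): c1 = 2.576, c2 = 2.290, overall = 0.0256. This does not reproduce the stated 0.05. Read as one-sided, the same pair gives 0.0251 and matches one-sided spending of 0.025 (0.0096 and 0.0442/2 = 0.0221). On that reading the two-sided final level is about 0.044.

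**Step 2: chance of a failed primary that meets the numeric gate.** This is overall(a1, 0.05) − overall(a1, a2), counting both tails.

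| Levels | Overall with 0.05 gate | Overall at own final level | Gap |
|---|---|---|---|
| Crossover as labelled | 0.0516 | 0.0256 | 0.0261 (from unrounded values) |
| Parallel | 0.0550 | 0.0496 | 0.0054 |

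If the crossover levels are really one-sided, the crossover gap shrinks to about the parallel size.

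For the crossover levels as labelled, with drift δ/(85/√124), the chance of the gap is 2.4% at the design effect of 30 m (drift 3.93), 10.8% at 20 m and 12.0% at 15 m. The last two effects are assumptions.

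**Step 3: direction.** The gate requires treprostinil to be superior, so only one tail opens it. By symmetry the null chance that it opens at either look is 0.0516/2 = 2.58% (crossover) or 0.0550/2 = 2.75% (parallel).

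**Step 4: family-wise error.** A false secondary claim through the gap also needs a secondary to reject. Under the global null, with the first secondary in the fixed order tested at 0.05 and both tails counted,

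family-wise error = overall(a1, a2) + P(gap and first secondary rejects).

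- Correlation 0: crossover 0.0256 + 0.05 × 0.0261 = 0.0269; parallel 0.0496 + 0.05 × 0.0054 = 0.0499.
- Correlation 0.9 (simulated): crossover about 3.7%; parallel about 5.2%.
- With the unrounded parallel pair (0.0193, 0.0442) the range over correlations 0 to 0.9 is about 5.0% to 5.2%.
- Ceiling at correlation 1, where every result in the gap counts: 5.16% and 5.50%.

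**The case against.** The strongest reply is that 7.7 already contains the right rule. Its first sentence makes a significant primary a necessary condition, and SAP 9.3 and protocol 10.3 and 10.3.3 agree. Under 4.2.2, a final p of 0.03 after a crossover interim is not significant, so on those statements no secondary is tested. The 0.05 may simply be the correct level for the default case without an interim. This stands in part: the plan is in conflict with itself and has not plainly adopted a 0.05 gate after an interim. It does not remove the problem, because the only sentence with a number says 0.05 and nothing says which statement prevails.

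Second, text following the gate sentence in 7.7 is blacked out and may set levels for the secondaries or deal with the interim. That limits what can be said about family-wise error. The gate sentence itself is complete and visible.

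Third, the path is doubly conditional. The interim is run only if recruitment is slow and at least 90% of the 6MWD data are present, and the trial must then continue to its final analysis. Without an interim, 0.05 is right. This limits how often the conflict would matter, but the path is prespecified and its rules should be consistent.

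A reader might also infer from the 5.2% and 5.5% totals that family-wise control at 5% fails in both designs. The documents do not support that. Those totals are two-tailed chances of meeting the numeric level, whereas the gate is directional and a false secondary claim needs a further rejection. For the crossover levels as labelled, the family-wise error stays well below 5% over the correlations examined, because the pair spends only 2.56%.

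**Conclusion.** The inconsistency is real and should be fixed, but it is not a serious failure of error control. After an interim, a primary that fails at its own final level can still meet the numeric gate in 7.7. The two-tailed null chance is about 2.6% for the crossover levels as labelled and about 0.5% for the parallel levels. Family-wise error is about 5.0% to 5.2% for the parallel levels, and about 2.7% to 3.7% for the crossover levels as labelled. If the crossover levels are one-sided, the small parallel figure applies there too.

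These figures assume 75% information at the interim, the global null, the first secondary tested at 0.05, and a primary-secondary correlation of 0 to 0.9. The documents give no correlation, and the level for the secondaries is not visible.

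The main reason to act is that the plan answers one question in two ways, and the choice would otherwise be made with the result in view.

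**What to change.** First settle whether 0.010 and 0.022 in SAP 4.2.2 are one-sided or two-sided. They match one-sided levels labelled as two-sided, so copying 0.022 into the gate now could carry a labelling error into 7.7.

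Then replace the numeric sentence in 7.7 with wording such as: *Secondary endpoints are formally tested only if the primary analysis shows superiority of treprostinil at the two-sided alpha allocated to that analysis, which is 0.05 if no interim efficacy analysis was conducted and otherwise the final-stage level in Section 4.2.2 (crossover) or Appendix 12.4.2 (parallel).*

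Repeat this in Appendix 12.4, and amend the 0.022 in Section 7 there so that it agrees with 12.4.2. Confirm that the levels for the secondaries are consistent with the new sentence.

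The cost is one sentence and its repeat in the appendix, with no change to the data or sample size. The gate becomes stricter if an interim is run: slightly if the final level is about 0.044, appreciably if it is 0.022. The change should be made before unblinding.
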